### **11.3. Reporting procedures**

#### **11.3.1. Reporting of Adverse Events (AEs)**

During the visits, the investigator will try to obtain, by means of examination or questioning the patient directly, all the information related to adverse events that have occurred.

All information regarding adverse events should be recorded in the corresponding section of the case report form. All adverse events occurring during the period covered will be recorded, from the moment the patient is included in the study (from signing of the consent form) up to 28 days after the last dose of the investigational product. When one or more signs or symptoms correspond to a disease, the main diagnosis or

syndrome will be reported. All adverse events will be followed up until resolution, stabilisation or until it is determined that study treatment or participation in the study was not the cause of the event. All adverse events that continue at the end of the study period should also be followed up to determine their final outcome.

### 11.3.2. Reporting Serious Adverse Events (SAEs)

All serious adverse events that occur during the trial, whether or not they are related to the study medication, must be reported immediately by email or by fax (completing the SAE form) within 24 hours of being reported by the investigator:

**ATT. SAFETY DEPARTMENT**  
**[contact]**  
**Email: [contact]**

The investigator will record the information regarding the SAE on the corresponding form. At least these **4 elements are mandatory** in order to report any adverse event:

- Name or identifier of the person **reporting** the SAE
- **Patient** number or identifier
- The **suspected drug** used in the trial: dose, route of administration, start and end date of treatment
- Information related to the **Adverse Event**:
  - Adverse Event term
  - Severity criteria
  - Assessment of causality

### 11.3.3. Reporting of Serious Adverse Events to the Health Authorities

It is the responsibility of the sponsor to notify the Health Authorities of all suspected serious and unexpected adverse reactions that have occurred in the clinical trial. This will be communicated within the time limits established in accordance with current regulations.

### 11.3.4. Monitoring of AEs and SAEs

After the initial AE or SAE report, the investigator is required to follow up on each case and obtain more information about its status. All AEs and SAEs documented on previous visits should be reviewed on subsequent visits. All AEs and SAEs must be evaluated until their resolution. This applies to all patients, including those who withdraw early.

The investigator will include in the follow-up any additional investigation that may clarify the nature and/or cause of the AE or SAE. This may include additional laboratory tests or investigations, histopathological examinations or consultation with other healthcare

professionals. Any co-investigator may request that the investigator carry out additional evaluations to clarify the nature and/or cause of the AE or SAE. If the patient dies during participation in the study or during an established follow-up period, the investigator will provide a copy of any post-mortem findings, including histopathology, that are requested.

#### **11.3.5. AEs or SAEs that occurred after the end of the study**

Post-study AEs or SAEs are defined as any event occurring outside the follow-up period defined in the protocol. The investigator is not required to actively search for the onset of AEs or SAEs that have occurred in patients who have participated in the clinical trial in the past. However, if at any time after a patient withdrew from the study the investigator should become aware of the existence of any AE or SAE, including the patient's death, that is deemed to be related to the study drug, the investigator should promptly notify the sponsor.

#### **11.3.6. Pregnancy and breastfeeding**

Study patients should be advised to notify the investigator immediately if they become pregnant during the study. Pregnant patients will stop receiving the study treatment. Patients will also be advised to report any pregnancy that occurred after the last visit if they believe conception occurred during their participation in the study.

A pregnancy in itself is not an AE unless there is a possibility that the investigational drug has interfered with the effectiveness of any of the contraceptive methods used. However, the investigator must notify pregnancies in accordance with the procedures and deadlines described for SAE reporting (section 11.3.2). The pregnancy reporting form should be used.

The pregnancy reporting forms must be submitted within 24 hours after the investigator becomes aware of the event:

**ATT. SAFETY DEPARTMENT**  
**[contact]**  
**Email: [[contact]](mailto:[contact])**

In accordance with local data privacy laws, the sponsor may request the contact information of the subject's doctor in order to follow the pregnancy until the outcome of the birth.

The pregnant patient or the patient's pregnant partner will be monitored until the end of the pregnancy. Any complications during pregnancy or lactation should preferably be reported as AEs. The outcome of the pregnancy must be reported on the pregnancy reporting form. Any miscarriage, stillbirth, birth defect/abnormality, death or other serious conditions of the baby should be reported and followed up as if it were an SAE.

*CONFIDENTIAL*

### **11.3.7. Overdose**

An overdose is defined as any dose greater than the highest dose included in the protocol. Consult the infusion guide for detailed instructions on preparing, storing and administering the investigational drug.

Any overdose should be noted in the CRF as an Adverse Event and the investigator must report them in accordance with the procedures and deadlines described for SAE reporting (section 11.3.2) if the overdose is related to a serious adverse event.

## **12. STATISTICAL CONSIDERATIONS**

### **12.1. General considerations**

This section describes the main analyses that will be carried out. The statistical analysis plan to be approved by the sponsor will include additional information on analyses, management of unavailable data and analytical methods. All data will be analysed with the SAS statistical analysis system. All analyses will be carried out mainly by descriptive statistical methods. Continuous endpoints will be described using mean and standard deviation, median, minimum, maximum, Q1 and Q3. Categorical endpoints will be described with frequencies and percentages as well as the exact 95% confidence interval of the relevant study variables. All results will be presented separately by treatment arm.

The final statistical analysis that will be the basis of the final report of the study will be done on the total population of 45 patients once the extension of the study has been completed. The data of the first 27 patients will be analysed in an intermediate statistical analysis.

### **12.2. Sample calculation**

The primary objective of the study is to evaluate the safety and toxicology profile of plitidepsin at each dose level administered once a day for 3 consecutive days.

Groups of 9 patients will be included and will be randomly assigned to each of the 3 arms. Depending on the safety analysis of each group of 3 patients included in each arm, it will be decided whether it is possible to include 3 more patients in the same arm, up to a maximum of 9 patients in each arm and a maximum of 27 patients in the study.

During the extension period of the study that will start after the recruitment of the 27 patients initially planned, an additional 18 patients will be included (6 at each dose level).

### **12.3. Analysis populations**

#### Safety population:

The population for the safety analysis will consist of all randomised patients who receive at least one dose (complete or not) of plitidepsin.

#### Efficacy population:

Patients are considered evaluable for efficacy if they have received all three doses of treatment and have completed a follow-up period of at least 2 weeks. Patients who do not complete the treatment period because the disease has evolved unfavourably will also be evaluable for efficacy.

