### **8.3. Replacement of subjects and reserve subjects**

Patients who sign the study consent and are not randomised will be replaced.

Patients who discontinue study treatment before the end of the three proposed administrations for reasons other than  $\geq$  grade 3 adverse events will be replaced.

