### **9.5. Management of infusion reactions (e.g. *hypersensitivity reaction*)**

In the event of a serious/life-threatening infusion reaction (grade  $\geq 3$ ), the plitidepsin infusion should be discontinued and immediate treatment with oxygen and bronchodilators should be considered. Treatment should be administered with diphenhydramine iv 50 mg or equivalent, hydrocortisone iv 100 mg and epinephrine (adrenaline) should be added if clinically indicated. The infusion should not be resumed and treatment with plitidepsin should be discontinued.

For mild or moderate/non-life threatening reactions (grade  $\leq 2$ ) such as allergic symptoms, the infusion should be stopped immediately and vital signs and pulse oximetry will be continuously monitored. Before resuming infusion of plitidepsin, iv dexamethasone 4 mg premedication (or equivalent) must be administered 20-30 minutes beforehand. If symptoms persist after stopping the infusion and administering dexamethasone, diphenhydramine 50 mg iv or equivalent and hydrocortisone 100 mg bolus iv or equivalent will be administered.

Symptoms and vital signs should be re-evaluated after 30 min. If they are normal or have improved, the infusion may be resumed at a third of the initial infusion rate during the first hour. Signs and symptoms should be continuously monitored during the infusion. Subsequently, the infusion rate could be increased according to tolerance. Any additional infusion will be started at a reduced infusion rate and IV prophylactic premedication will be administered as described above. The patient will be monitored during the first hour after the infusion to detect symptoms. If no hypersensitivity reactions are observed, the

infusion rate could be increased again. In any case, if symptoms do not improve after 30 minutes, anti-H1 and/or corticosteroids will be administered until resolution, and treatment with plitidepsin will be discontinued.

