4 STUDY POPULATION

4.1 Definition of the study population to be analyzed

The safety population will include all enrolled/randomized patients who received at least one dose (full or not) of plitidepsin.

The efficacy population will include all patients who have received all three doses of treatment and have completed a follow-up period of at least 2 weeks. Those patients who did not complete the treatment period due to the unfavorable evolution of the disease will be also included in for the efficacy population.

[figure not shown]

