9.3 Treatment

The listing "Treatment" will include the following information:

- Center
- Patient id.
- Treatment arm (Arm A; Arm B; Arm C)
- Treatment administration (Yes/No).
 - If so, reasons will be detailed.
- Administered doses
- Treatment interruption (Yes/No).
 - If so, the reasons will be indicated.
- Pre-medication (Yes/No). If so, it will be indicated:
 - Type (antiemetic, gastric protector, antihistamine and corticosteroids)
 - Code (ATC)

- Active substance
- Dose
- Route of administration
- Units
- Days on treatment with plitidepsin
- Total dose of plitidepsin administered (sum of daily doses - mg)
- End of treatment date
- End of treatment (Treatment completed according to protocol; Withdraw informed consent; Non related adverse event; Adverse reaction to plitidepsin; Death; Investigator's decision; Administration of prohibited medication; Other).
 - If the adverse event is not related to the drug, the description of event and grade will be provided (1; 2; 3; 4; 5; Not available).
 - If the adverse event is related to the drug, the description of event and grade will be provided (1; 2; 3; 4; 5; Not available).
 - If it is Investigator's decision: specify
 - If other: specify

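### The efficacy set drops patients who stop plitidepsin for toxicity but keeps those who stop because COVID-19 worsened, and the SAP has no code or rule to identify the second group

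*Protocol*

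**What the plan says.** Protocol 12.3 sets the main condition, with the follow-up counted in weeks: "Patients are considered evaluable for efficacy if they have received all three doses of treatment and have completed a follow-up period of at least 2". Its only exception is for disease: "Patients who do not complete the treatment period because the disease has evolved unfavourably will also be evaluable for efficacy". SAP 4.1 repeats the rule: "Those patients who did not complete the treatment period due to the unfavorable evolution of the disease will be also included". Neither document defines unfavourable evolution or names the data field that decides it. Protocol 12.5.1 and SAP 8 run the efficacy analyses on this set.

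Protocol 9.5 supplies a route to early stopping for toxicity. After an infusion reaction of grade 3 or above, "The infusion should not be resumed and treatment with plitidepsin should be discontinued". Treatment also ends after a milder reaction that does not improve.

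Protocol 8.3 covers replacement: "Patients who discontinue study treatment before the end of the three proposed administrations for reasons other than" adverse events of grade 3 or higher are replaced.

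The end-of-treatment reasons in SAP 9.3 include "Non related adverse event; Adverse reaction to plitidepsin; Death", followed by investigator's decision, prohibited medication and a free-text category. None of them names worsening COVID-19.

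**The concern.** Take two patients whose treatment ends after the same dose, one for a drug reaction and one for worsening COVID-19. Both can be followed to the final visit, yet only the second counts for efficacy. What separates them is an event after the start of treatment that may itself depend on dose, attributed by an investigator who knows the dose (Protocol 7.4: masking not applicable).

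Each arm's efficacy summary is then conditional on tolerating three doses, or on stopping for disease reasons. This matters because Protocol 6.1 selects the recommended dose from safety and efficacy together, by dose level. If stopping for toxicity differs between arms, the efficacy columns being compared no longer describe the patients who were given each dose.

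**Working it through.** **Planned size.** Nine per arm plus six in the extension is 15, and 3 × 15 = 45, as Protocol 6.1 states. No power calculation lies behind this figure.

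**What happens to a patient who stops after one or two doses** (Protocol 8.3 and 12.3, SAP 4.1 and 9.3):

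| Reason for stopping | In efficacy set | Replaced | End-of-treatment code |
|---|---|---|---|
| Drug reaction, grade 3 or above | No | No | Own code, with event and grade |
| Drug reaction, grade 1–2 | No | Yes | Own code, with event and grade |
| COVID-19 worsening, with a grade 3 or higher event | Yes | No | None |
| COVID-19 worsening, without such an event | Yes | Yes | None |

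A stop for worsening disease must be filed as a non-related event, death, investigator's decision or other. It then has to be recovered from free text or from the adverse event form, where SAP 9.4 records relationship and action taken. That second route is incomplete. Protocol 11.2.5 keeps some disease-related changes off the adverse event form, and Protocol 12.5.2 and SAP 7.1 count an event as related when a relationship cannot be ruled out. A doubtful respiratory event could therefore be placed on either side.

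**Chance of at least one toxicity stop.** The documents give no rate, so p is an assumption. The chance is 1 − (1 − p)^n.

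| Assumed p | Arm of 15 | All 45 |
|---|---|---|
| 2% | 26% | 60% |
| 5% | 54% | 90% |
| 10% | 79% | 99% |
| 20% | 97% | about 100% |

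One stopper is 1/15 = 6.7% of an arm, two are 13.3% and three are 20%.

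The nearest figure in the documents is in Annex 7: grade 3/4 hypersensitivity in 18 of 822 adults (2.2%). Applied here it gives 15 × 18/822 = 0.33 per arm and 45 × 18/822 = 0.99 overall. It is a rate of one kind of event in earlier plitidepsin trials, not a rate of stopping in this one.

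**Effect on a reported proportion.** Let k patients in an arm of 15 stop for toxicity without replacement, and let x events occur among the 15 − k retained. The plan reports x/(15 − k). The all-treated value lies between x/15, if no stopper has the event, and (x + k)/15, if all do. With x = 2:

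| k | Reported | All-treated range |
|---|---|---|
| 1 | 2/14 = 14.3% | 13.3% to 20.0% |
| 2 | 2/13 = 15.4% | 13.3% to 26.7% |
| 3 | 2/12 = 16.7% | 13.3% to 33.3% |

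The reported value falls inside the range each time, so the error can have either sign. For k = 2 the exact 95% interval around 2/13 is 1.9% to 45.4%.

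**Effect on precision.** With no events, the exact 95% upper limit is 21.8% for 15 patients, 23.2% for 14, 24.7% for 13 and 26.5% for 12.

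**The case against.** Four objections carry weight.

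- **Coding.** A reader might infer that the two kinds of stop cannot be distinguished at all. The documents do not support that. Stops attributed to plitidepsin have their own code with event and grade, and the adverse event listing separates plitidepsin from study disease. What is missing is a code and a derivation rule for the disease-related stops.
- **Direction and size.** A reader might infer that the most toxic dose will look more effective. That requires stoppers to do worse than completers, and nothing in the documents shows it. Annex 7 says the hypersensitivity cases reversed quickly once the infusion was stopped and supportive measures were given. At 18/822, three or more stops in an arm of 15 have a chance of about 0.4%. Annex 7 also places muscle symptoms weeks after the start of treatment, typically too late to cut short a three-day course.
- **Replacement.** It is tempting to count the refusal to replace grade 3 or higher stops as a second fault. Those patients remain in the safety population, and safety is the primary objective, so the rule fits its purpose.
- **Visibility.** Non-completion and its reasons are part of the primary endpoint. SAP Table 10.1.1 shows both populations by dose, SAP 14 lists the patients excluded from efficacy, and deaths are tabulated by dose in SAP Table 11.5.5. Two grade 3 or higher patients in an arm already trigger a recruitment interruption and joint review with the agency (drug-related events in the extension). Efficacy is secondary and descriptive.

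These points limit the consequence but do not repair the definition. A listing of exclusions does not correct a summary table, and no planned table gives IMV, ICU, NIMV, oxygen or viral-load results by arm in all treated patients. The numbers at risk under SAP Figure 15.1.2 sum to 45 (6 + 23 + 16), which suggests few exclusions. That figure does not name its population, however, so it cannot settle the matter.

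**Conclusion.** The point holds as a flaw in how the efficacy set is defined. Patients who stop for toxicity are excluded from the efficacy summaries by an event that follows treatment and may depend on dose, and the set's single exception rests on a judgement that the SAP neither codes nor defines.

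The likely effect is modest: roughly zero or one patient per arm if the stopping rate is near 2%, and more if it is higher. With 15 per arm, even one patient moves a proportion by several percentage points, in a direction that cannot be known beforehand. The safety conclusions are unaffected. The exposure is confined to the efficacy half of the dose selection, mainly IMV/ICU, NIMV, oxygen and viral load, since deaths are also reported in the safety tables.

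The sizes rest on assumed stopping rates and on no replacement of the stoppers. Stops for grade 1–2 reactions are replaced, which restores the count but not the comparability.

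**What to change.** Present mortality, IMV/ICU, NIMV, oxygen therapy and viral-load change by arm in all patients who received any plitidepsin, that is, the safety population already defined in Protocol 12.3 and SAP 4.1. Keep the current efficacy set as a supportive analysis.

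Add a coded end-of-treatment reason for unfavourable evolution of COVID-19, state in the SAP how it is assigned, and derive membership of the supportive set from that code alone. Protocol 8.3 needs no change.

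The cost is a rerun of existing table shells and one added code. Protocol 10 already schedules viral load, PCR and vital signs with oxygenation to Day 31, and stopping for toxicity is not among the reasons for study withdrawal in Protocol 8.1. The one drawback is that partly dosed patients may slightly dilute any sign of activity, and the supportive set remains available to show that.

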### **12.4. Analysis of the primary endpoint**

The safety analysis will be performed in the safety population, that is, in patients who have received at least one dose of treatment. Patients will be analysed in the administered treatment arm.

Safety and tolerability analyses will be presented by treatment arm as well as by treatment arm according to age group (<65 years; ≥65 years). Adverse events will be coded using the latest version of the MedDRA dictionary and assessed using the NCI-CTCAE criteria v. 5.0.

The number and percentage of patients presenting the following ≥ grade 3 adverse events will be provided, according to the NCI-CTCAE criteria v. 5.0 at 3, 7, 15 and 31 days after the start of study treatment:

- Haematological
    - Neutropenia
    - Thrombopenia
    - Anaemia
    - Lymphopenia
  - Non-haematological
    - CPK increase
    - ALT and/or AST increase
    - Total bilirubin or direct bilirubin increase
    - Neurotoxicity
    - QT-QTc interval prolongation
  - Other ≥ grade 3 adverse events
- The number and percentage of patients in whom treatment cannot be completed and the reasons will be provided.
  - The number and percentage of patients with AEs and SAEs will be provided at 3, 7, 15 and 31 days.
  - The evolution of haematological and non-haematological parameters from the baseline visit on days 3, 7, 15 and 31 will be provided.

*CONFIDENTIAL*

- The number and percentage of patients with ECG abnormalities on days 1, 2, 3, 4, 5, 6, 7, 15 and 31 will be provided. Any alterations detected will be described in detail.

## **12.5. Analysis of secondary endpoints**

### **12.5.1. Efficacy assessments**

Efficacy analyses will be performed on the efficacy population defined above. For the evaluation of efficacy endpoints, the following analyses will be carried out separately for each dosage level:

- The evolution of the viral load from the baseline visit on days 3, 4, 7, 15 and 31 will be provided.
- The time to negative detection of COVID-19 by PCR will be calculated as the time that elapses in days from the date of randomisation to the first date of PCR with a negative result. The time to negative detection will be analysed following the Kaplan-Meier methodology, providing the median and the corresponding 95% confidence interval.
- The number and percentage of patients who die 7, 15 and 31 days after starting the treatment with plitidepsin shall be described.
- The number and percentage of patients who require mechanical ventilation and/or ICU admission at 7, 15 and 31 days will be provided.
- The number and proportion of patients requiring invasive mechanical ventilation shall be stated.
- The number and proportion of patients requiring non-invasive mechanical ventilation shall be stated.
- The number and proportion of patients requiring oxygen therapy shall be stated.

